### **8.3.1.2 Event-free Survival at 12 Months**

Event-free survival will be evaluated using the time in months from transplant to either the first event or their last evaluation calculated as:

$$12 * (\text{date of event/last evaluation} - \text{date of transplant}) / 365.25,$$

or, for HSCT control subjects for whom the dates were not recorded, as:

$$\text{age in months at death/end of follow-up} - \text{age in months at transplant}.$$

For the purpose of this analysis, the events of interest are:

- death;
- reinstitution of PEG-ADA ERT;
- requirement for a second transplant.

Event-free survival will be summarized in the same way as overall survival described in Section 8.3.1.1.

In addition, if there are any events (other than death), the time to each event will be summarized in a similar manner to the overall event-free survival.

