## 8.3 Efficacy Analyses

The primary comparison for all efficacy analyses will be between the IMP treated on-study subjects and the allogeneic HSCT controls treated at GOSH without a matched related donor. Secondary comparisons will be between:

- the IMP treated on-study subjects and the HSCT controls treated at GOSH with a matched related donor;
- the IMP treated on-study subjects and the total group of HSCT controls;
- all IMP treated subjects (on-study and CUP) and the HSCT controls treated at GOSH without a matched related donor;
- all IMP treated subjects (on-study and CUP) and the HSCT controls treated at GOSH with a matched related donor;
- all IMP treated subjects (on-study and CUP) and the total group of HSCT controls.

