### 8.3.1 Primary Efficacy Endpoints

#### 8.3.1.1 Overall Survival at 12 Months

Overall survival will be evaluated using the time in months from transplant to either the subject's death or their last evaluation calculated as:

$$12 * (\text{date of death/last evaluation} - \text{date of transplant}) / 365.25,$$

or, for HSCT control subjects for whom the dates were not recorded, as:

$$\text{age in months at death/end of follow-up} - \text{age in months at transplant}.$$

The number (%) of subjects who were still alive at 12 months post-transplant will be summarised. For the purpose of this analysis, any subject who withdrew from the study prior

to 12 months, who was known to be alive at the last evaluation, will have a status of “unknown”. The proportion and exact 95% confidence interval (CI) for survivors at 12 months post-transplant will be calculated for each of the IMP treated and HSCT control groups along with the difference in proportions (with 95% CI) between the IMP treated and control groups, excluding those with unknown status.

Overall survival in each treatment group will also be represented using a Kaplan-Meier curve for time to death. For the purpose of this analysis, any subject who withdrew from the study prior to 12 months and was known to be alive at the last evaluation will be censored at the date of their last evaluation. If appropriate, the proportion alive at 12 months and the associated 95% CI will be estimated for each treatment group from the Kaplan-Meier curve along with the median survival time (and interquartile range), if they can be estimated from the data.

If there is at least one event in each group, the log-rank test will be used to compare the difference in survival curves between the IMP treated and HSCT control groups.

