## **8.3.2 Secondary Efficacy Endpoints**

### **8.3.2.1 Overall and Event-free Survival at 2 and 3 Years**

Overall and event-free survival at 2 and 3 years will be summarized in the same way as for the analyses at 12 months described in Sections 8.3.1.1 and 8.3.1.2.

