### 8.3.2.2 Use of Immunoglobulin Replacement Therapy

The time to cessation of IgRT will be calculated (in months) as:

$12 * (\text{stopping date of IgRT} - \text{date of transplant}) / 365.25$ ,

or, for HSCT control subjects for whom the dates were not recorded, as:

age in months when IgRT stopped – age in months at transplant.

Time to cessation of IgRT will be summarised for each of the IMP treated and HSCT control groups using descriptive statistics and, if appropriate, estimated from a Kaplan-Meier curve in which subjects who are still receiving IgRT will be censored at the time of their last visit.

The number (%) of subjects who have stopped treatment with IgRT at 12, 18, 24, 30 and 36 months without restarting at any subsequent time point will be summarized for each of the IMP treated and HSCT control groups (data permitting) along with exact 95% CIs.

In addition, serum immunoglobulin levels (IgG, IgA and IgM) will be measured at each visit for the IMP treated subjects. Levels of IgG, IgA and IgM and changes from baseline will be summarised by visit using descriptive statistics. In addition, plots of the median value and range over time on a logarithmic scale will be produced for each parameter along with individual plots for each subject which will include age-dependent normal ranges provided by the study site.

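### For HSCT controls without recorded dates, the event-free survival formula is the overall-survival formula and leaves out PEG-ADA restart and second transplant

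*SAP*

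**What the plan says.** SAP 8.3.1.2 says EFS is evaluated using the "time in months from transplant to either the first event or their last evaluation" and lists three events: death, reinstitution of PEG-ADA and requirement for a second transplant. The formula for subjects with dates follows this and runs to the "date of event/last evaluation". For HSCT controls whose dates were not recorded, the time is instead "age in months at death/end of follow-up" minus age in months at transplant. The section adds that "if there are any events (other than death), the time to each event will be summarized" in a similar manner.

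The undated formula for OS in SAP 8.3.1.1 has the same wording as the undated EFS formula. The dated formulas differ between the two sections: OS uses the date of death where EFS uses the date of the event.

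The primary comparison in SAP 8.3 sets the on-study gene therapy subjects against "the allogeneic HSCT controls treated at GOSH without a matched related donor". EFS is handled like OS, for which SAP 8.3.1.1 states: "If there is at least one event in each group, the log-rank test will be used". SAP 8.3.2.1 has EFS at 2 and 3 years "summarized in the same way as for the analyses at 12 months".

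**The concern.** The undated formula contradicts the definition it is meant to implement. It measures time to death or end of follow-up, so for an undated control EFS time equals OS time whatever non-fatal failures occurred. Nor can it supply the time to each non-fatal event, which the same section asks for.

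The SAP's other undated formulas show that this is not a deliberate convention. For immunoglobulin cessation, 8.3.2.2 uses "age in months when IgRT stopped", and 8.3.3.1 likewise uses the age at which PEG-ADA stopped. In 8.3.1.2 it appears that the dated line was adapted from OS to EFS and the undated line was carried over unchanged.

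What is at stake is a primary endpoint. A control whose graft failed could be reported as event-free, with control EFS too high, Kaplan-Meier event times too long and the comparison tilted against the gene therapy. Protocol 8.9.2 calls the comparison descriptive but also specifies a log-rank test. A descriptive estimate built on the wrong event time is wrong in any case.

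**Working it through.** The documents give no figure to reproduce, because neither the number of controls nor their outcomes are stated. The check compares the formulas, applies the rule literally to assumed patients, and sizes the effect on assumed group sizes.

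**1. Formulas (SAP 8.3.1.1 and 8.3.1.2)**
- OS, dated: date of death or last evaluation minus date of transplant. OS, undated: age at death or end of follow-up minus age at transplant.
- EFS, dated: date of event or last evaluation minus date of transplant. EFS, undated: identical to OS, undated.

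Example (assumed): transplant at age 6 months, second transplant at 10 months, alive at end of follow-up at 66 months. As written, EFS time = 66 − 6 = 60 months, the same as OS. By the section's definition it is 10 − 6 = 4 months.

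**2. Status at 12/24/36 months under the literal rule**

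Times are months after transplant. The formula does not state the event indicator, so two are tried: L (any listed event) and D (death only).

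| Assumed control | By definition | Literal, L | Literal, D |
|---|---|---|---|
| Failure 3, alive at 120 | event/event/event | free/free/free | free/free/free |
| Failure 15, alive at 120 | free/event/event | free/free/free | free/free/free |
| Failure 3, death 18 | event/event/event | free/event/event | free/event/event |
| Failure 3, last seen alive 30 | event/event/event | free/free/event | free/free/unknown |
| Failure 3, last seen alive 10 | event/event/event | event/event/event | unknown/unknown/unknown |
| Failure 3, death 10 | event/event/event | event/event/event | event/event/event |

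When the failure precedes a landmark and death or end of follow-up comes after it, the control is wrongly event-free at that landmark under either indicator. When a failed control is last seen alive before the landmark, the result depends on the indicator.

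**3. Size on the 12-month proportion (N assumed)**

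Shift per misclassified control = 100/N points: 100/10 = 10.0; 100/20 = 5.0. With exact (Clopper-Pearson) 95% intervals:
- N = 10: 6/10 = 60% (26.2–87.8%) becomes 7/10 = 70% (34.8–93.3%).
- N = 20: 12/20 = 60% (36.1–80.9%) becomes 13/20 = 65% (40.8–84.6%).

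**4. Log-rank illustration (all data assumed)**

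Gene therapy: 10 subjects, one event at month 9, nine censored at 36. Controls: 10 patients, deaths at months 1, 2 and 4, one undated non-fatal failure at month 3, and six event-free. The failed control and the six event-free controls are all followed to month 60.

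- By definition: expected gene therapy events = 10/20 + 10/19 + 10/18 + 10/17 + 10/16 = 2.795, observed 1; chi-square 2.635, p = 0.105. Control Kaplan-Meier EFS at 12 months = 0.60.
- Literal rule, failed control timed at 60: expected = 10/20 + 10/19 + 10/18 + 10/17 = 2.170, observed 1; chi-square 1.385, p = 0.239. Control EFS at 12 months = 0.70.

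The literal result is the same under L and D, because no gene therapy subject is still at risk at month 60.

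**The case against.** The strongest reply is that the section already supplies the right rule. The governing sentence, the dated formula and the event list all point to first event, and Protocol Appendix 8 section 5 names the same two non-fatal events. A programmer would have to override all of that to apply the OS line. This stands as far as intent goes: it is a drafting slip, not proof of a wrong analysis. But an explicit formula that conflicts with the definition leaves a primary endpoint to the programmer's choice.

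Second, there may be no undated controls. SAP section 10 shows that the undated calculations were clarified in version 11.0, which also brought in external controls, and that version 12.0 restricted controls to GOSH. A link between those two version 11.0 changes is only an inference. Appendix 8 section 3 plans to collect dates of birth, death and treatment(s), which should normally date a second transplant and leave PEG-ADA restart as the main exposure. This also stands: the number affected is unknown and could be zero. Against it, version 12.0 kept the rule, and SAP 8.2.15 and 8.2.16 have age at transplant and duration of follow-up recorded on the eCRF for controls.

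Third, the 12-month count could be taken directly from patient records and not from the computed time. That is possible in practice, but 8.3.1.2 says EFS is evaluated from the time, so the text does not support it.

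Finally, the sizes are hypothetical, the assumed log-rank example does not cross 0.05 in either form, and any bias cannot flatter the gene therapy. All true; these points bear on severity, not on whether the formula is wrong.

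**Conclusion.** The concern holds. The undated EFS formula for HSCT controls is wrong as written, and no other passage in the protocol or SAP corrects it. Confidence in the mismatch is high; the numerical consequence cannot be determined from the documents. It depends on how many controls lack dates and, among them, how many had a non-fatal failure before a landmark with death or end of follow-up after it. Where that occurs, control EFS is overstated by 100/N points per patient. The figures for N of 10 and 20 and the log-rank example are illustrations only. The HSCT outcome figures in Protocol 3.2.1 show that non-fatal graft failure happens, but they do not bound the effect here.

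This should be fixed before the comparison is run: the endpoint is primary, the rule carries to 2 and 3 years, and the correction is small. It is not rated higher because the section's intent is clear and the number affected may be zero.

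**What to change.** - In SAP 8.3.1.2, replace the undated formula with: age in months at first event (death, PEG-ADA reinstitution or second transplant), or at end of follow-up if event-free, minus age in months at transplant. The list of EFS events stays as it is.
- Add one sentence saying that the event indicator follows the same first-event list.
- Confirm that the HSCT eCRF, which is not among the documents, captures the age or date of PEG-ADA restart and of second transplant. Appendix 8 section 3 names only previous PEG-ADA, while SAP 8.2.15 reports enzyme replacement after transplant as a number and percentage. This is a query; no gap is shown.
- Optional: if a failure is known but its age is not, report best-case and worst-case EFS at each landmark.

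The cost is one formula, one sentence and a check of two data items. Obtaining those items relies on the re-consent and record access already planned in Appendix 8.

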## **3.2 Management options for ADA-SCID**

### **3.2.1 Haematopoietic stem cell transplantation for ADA-SCID**

Haematopoietic stem cell transplantation (HCST) is the treatment choice that is most widely available to most physicians and transplant centres. Until recently, data on the outcome of ADA-SCID transplants has been limited as most SCID transplant papers have presented data on the outcome of all SCID types rather than by specific molecular defect (Antoine et al., 2003). For these reasons, a multicenter retrospective study gathering data on outcome of haematopoietic stem cell transplantation for ADA-SCID has been conducted. In this study, we analysed outcome of HSCT in 106 patients with ADA-SCID who received a total of 119 transplants.(Hassan, 2012 )

Donor source had a major impact on the outcome of HSCT (fig 1). Overall survival was higher in Matched Sibling Donor (MSD) and Matched Family Donor(MFD) HSCTs (86% (42 patients) and 81% (12 patients) respectively). Comparison of survival outcomes in MisMatched Unrelated Donor (MMUD) and haploidentical transplants [29% (7 patients) and 43% (30

patients) respectively] to those of MSD HSCT showed a highly significant difference ( $p<0.0001$ ). Comparison of overall survival in MSD to MUD HSCT also showed a significant difference ( $p<0.05$ ). In haploidentical transplants, even though overall survival was 43%, stable engraftment was only noted in 11 (37%) patients. The majority of deaths in the Matched Unrelated Donor (MUD), MMUD and haploidentical transplants (HAPLO) were in the first 100 days after HSCT, with relatively few late deaths. The causes of death were mainly related to pneumonitis/respiratory failure and sepsis which formed over 50% of all deaths. Other major causes included graft versus host disease (15%) and fungal infection (11%).

**Figure 1:** Kaplan-Meier curve showing overall survival in relation to donor source. MSD—matched sibling donor; MFD—matched family donor; MUD—matched unrelated donor; MMUD—mismatched unrelated donor; HAPLO—haploidentical donor (data from manuscript in preparation).

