### HSCT Control Patients

The primary efficacy population from the HSCT historical control cohort will consist of ADA-SCID patients without a medically eligible HLA-matched sibling/family donor and treated with HSCT at Great Ormond Street Hospital (GOSH) from the year 2000 onwards.

Secondary efficacy populations will comprise:

- ADA-SCID patients with matched related donors treated with HSCT at GOSH from the year 2000 onwards;
- the complete HSCT historical control cohort consisting of ADA-SCID patients with any type of donor treated with HSCT at GOSH from the year 2000 onwards.

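### Kaplan-Meier curves for PEG-ADA restart and second transplant, read as risks, overstate these failures wherever children die first; cumulative incidence by first-event type should replace them

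*SAP*

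**What the plan says.** SAP 8.3.1.2 defines three EFS events: death, return to PEG-ADA and need for a second transplant. For the composite, "Event-free survival will be summarized in the same way as overall survival described in Section 8.3.1.1". For the two non-fatal components, and only if any such events occur, "the time to each event will be summarized in a similar manner to the overall event-free survival".

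The method inherited from SAP 8.3.1.1 has four parts:

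- a crude number and percentage at 12 months with an exact 95% CI, leaving out children of unknown status;
- a Kaplan-Meier curve ("Overall survival in each treatment group will also be represented using a Kaplan-Meier curve for time to death");
- if appropriate, a 12-month proportion read from that curve;
- a group comparison: "If there is at least one event in each group, the log-rank test will be used".

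On timing, "Event-free survival will be evaluated using the time in months from transplant to either the first event or their last evaluation". The only written censoring rule is that "any subject who withdrew from the study prior to 12 months and was known to be alive at the last evaluation will be censored"; the censoring time is that evaluation. For transplant controls without recorded dates, the EFS time is age at death or end of follow-up minus age at transplant.

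SAP 8.3.2.1 applies the same methods at 2 and 3 years. Neither document mentions cumulative incidence or competing risks.

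**The concern.** In composite EFS, death is one of the events, so Kaplan-Meier is sound. In a curve for PEG-ADA restart alone, death is not the event, yet it makes the event impossible. The timing rule offers only an event time or a last-evaluation time, so a child who dies first can enter only as censored. Kaplan-Meier then treats that child as if still able to restart later.

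The breakdown would be used to see whether an EFS difference comes from deaths or from graft failure. The groups may differ most in mortality. The primary transplant comparator is "ADA-SCID patients without a medically eligible HLA-matched sibling/family donor" (SAP 7.1), and the protocol's background (3.2.1) reports that "The majority of deaths in the Matched Unrelated Donor (MUD), MMUD and haploidentical transplants (HAPLO) were in the first 100 days after HSCT". A percentage whose bias depends on mortality is therefore a poor tool for that comparison. Where transplant mortality is the higher, the error makes transplant graft failure look more frequent than it was, which favours gene therapy. The component percentages also cannot be added to the deaths to recover the EFS failures.

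**Working it through.** The documents give no planned figure for this analysis, so there is none to reproduce.

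**Inputs from the documents.** Survival in the multicentre transplant series (Protocol 3.2.1): matched sibling 86%; matched unrelated 66% of 15, which agrees with 10/15 = 66.7%; haploidentical 43% of 30; mismatched unrelated 29% of 7. Survival in earlier gene therapy trials: 100% of 36 (Protocol 3.2.5, Table 1).

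**Assumptions.** The documents give neither mortality nor restart rates for the study's own (GOSH) controls. I assume a Kaplan-Meier component risk of 20% or 30% at one year, and I treat the survival figures as one-year values.

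**Step 1: counts.** Take 15 controls with 5 early deaths, after which 3 of the 10 survivors restart PEG-ADA.

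- One minus Kaplan-Meier, deaths censored: 1 − (9/10)(8/9)(7/8) = 3/10 = 30%.
- Actual incidence: 3/15 = 20%.
- Sum with deaths: 5/15 + 3/15 = 8/15 = 53.3%, which equals the composite EFS failures. With the Kaplan-Meier figure the sum is 33.3% + 30% = 63.3%.

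In this example every death precedes every failure. That ordering gives the largest excess, a factor of 1/survival = 15/10 = 1.5. If every failure came first, the two methods would agree.

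**Step 2: constant hazards.** Let a = −ln(1 − Kaplan-Meier risk) and b = −ln(survival). The actual one-year incidence is a/(a + b) × [1 − exp(−(a + b))]. At 30% risk and 33% mortality, a = 0.357 and b = 0.400, so the incidence is 0.357/0.757 × (1 − 0.70 × 0.67) = 0.471 × 0.531 = 25.0%.

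**Step 3: deaths confined to the first 100 days.** Let T = 100/365.25 and h = b/T. The incidence is a/(a + h) × [1 − exp(−(a + h)T)] + exp(−(a + h)T) × [1 − exp(−a(1 − T))].

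| Assumed survival | KM risk 30%: constant hazards | KM risk 30%: deaths by day 100 | KM risk 20%: constant hazards | KM risk 20%: deaths by day 100 |
|---|---|---|---|---|
| 100% | 30.0% | 30.0% | 20.0% | 20.0% |
| 86% | 28.0% | 26.4% | 18.6% | 17.6% |
| 66% | 24.9% | 21.3% | 16.5% | 14.1% |
| 43% | 20.8% | 15.2% | 13.7% | 10.1% |
| 29% | 17.8% | 11.4% | 11.7% | 7.5% |

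The cells are actual incidences. Kaplan-Meier would show 30% or 20% in every row.

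**Step 4: effect on a comparison.** Ten children with no deaths and 2 failures give 20% by both methods. Ten children with 4 early deaths and 2 later failures give 2/6 = 33% by Kaplan-Meier and 2/10 = 20% in fact. The same proportion failed in each group, but the curves would show 20% and 33%.

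**The case against.** Several points on the other side stand.

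- **Censoring of deaths is not written in the SAP.** A reader might infer that the plan says to censor children who die. Its one censoring rule covers children who withdrew alive, and the component sentence asks only for a similar manner. Censoring follows from using Kaplan-Meier with the stated timing; the text itself is silent.
- **Other outputs show the actual counts.** The inherited method begins with a crude proportion. Because only children who withdrew alive are of unknown status, that rule does not remove a dead child. In the 15-child example the crude figure would be 3/15 = 20% if the dead are kept in the denominator, though the SAP does not say how they are classified. SAP 8.2.15 also counts controls receiving enzyme replacement after transplant, and SAP 8.4.1.3 lists deaths.
- **The log-rank test is not invalid.** With deaths censored it compares cause-specific hazards, the rates among children still alive and event-free. In Step 4 those rates do differ. The error arises only when the curve or its percentage is read as a risk.
- **The analysis is supplementary.** It is produced only if non-fatal events occur, with 10 on-study subjects, and Protocol 8.9.2 calls the comparisons with historical controls descriptive.
- **The size is assumed.** The mortality figures come from a multicentre series, not from the study's own controls treated since 2000, and the restart risks are not in the documents.

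These points limit the weight of the concern. They do not remove it: the Kaplan-Meier component curves are planned, would be read as risks, and would be wrong as risks wherever deaths precede failures.

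**Conclusion.** The point holds for the component Kaplan-Meier curves and any percentages read from them, at 12 months and at 2 and 3 years. One minus Kaplan-Meier overstates PEG-ADA restart and second transplant when children die first. The overstatement is larger where early mortality is higher and nil where no child dies.

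The size for the study's own controls is unknown. At an assumed 33% mortality and 30% Kaplan-Meier risk, the actual incidence is about 20% (all deaths before all failures) to 25% (constant hazards). The gap would shrink further if failures tended to precede deaths.

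A reader might go on to infer that the primary EFS comparison is biased against transplant. The documents do not support that: overall survival and composite EFS both count death as an event and are unaffected by this problem. The change is worth making before analysis, but it concerns a secondary breakdown, not the primary result.

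**What to change.** In SAP 8.3.1.2, and through it 8.3.2.1:

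- Replace the component Kaplan-Meier curves and percentages with Aalen-Johansen cumulative incidence by first-event type, with death, PEG-ADA restart and second transplant as mutually competing first events. Give 95% CIs at 12, 24 and 36 months. Treating death alone as the competing event would not be enough, because a child who restarts PEG-ADA and later has a second transplant or dies would be counted twice. With first-event types, the components sum to the EFS failures.
- State that children who die without the component event stay in the denominator of the crude component proportion, as not having had that event.
- Describe any log-rank test on a component as a comparison of cause-specific hazards.
- For controls without dates, use age at the event where available, not age at death or end of follow-up. Otherwise the new curves inherit wrong event times.
- Keep Kaplan-Meier for overall survival and composite EFS.

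The cost is a little extra programming, plus retrieval of event ages for undated controls. A second transplant that follows a PEG-ADA restart will not appear in the first-event curves; the crude proportions can still show it.
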